4. STUDY ENDPOINTS AND DEFINITIONS

4.1 PRIMARY ENDPOINT

1. Proportion of children who complete COVID-19 vaccination, as verified in state, clinic, or participant-held records

Def: Completion of COVID-19 vaccination will be coded as 1=Yes or 0=No. Verification of vaccine receipt will occur by any of the following methods:

- Photograph of the child's vaccine card, furnished by the caregiver
- Medical records documentation of child vaccine receipt
- Recorded vaccine receipt in the appropriate state vaccine registry

4.1 SECONDARY ENDPOINTS

1. Proportion of children who receive ≥ 1 dose of the COVID-19 vaccination series, as verified in state, clinic, or participant-held records

Def: Initiation of the COVID-19 vaccination series will be coded as 1=Yes or 0 = No. Verification of vaccine receipt will occur by any of the following methods:

- Photograph of the child's vaccine card, furnished by the caregiver
- Medical records documentation of child vaccine receipt
- Recorded vaccine receipt in the appropriate state vaccine registry

2. Change in enrolled parent/caregiver domain scores from baseline to week 16 on the modified SAGE Vaccine Hesitancy Scale adapted for the COVID-19 Vaccine

Def: The modified SAGE Vaccine Hesitancy Scale includes ten statements with ordinal responses using a 5-point Liker scale (1 = Strongly Disagree; 2 = Somewhat Disagree; 3 = Neutral; 4 = Somewhat Agree; 5 = Strongly Agree). A composite vaccine hesitancy score will be the sum of the 10 items/statements after reverse coding items 1, 2, 3, 4, 6, 7, and 8 (range of 10 to 50). The reverse coding makes directionality uniform across the ten items so that a higher composite score indicates more hesitancy.¹⁰ Additionally, each statement/item will be treated as an individual outcome measure of hesitancy (range of 1 to 5).

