## 1. PROTOCOL SUMMARY

### 1.1 SYNOPSIS

Title:	Improving pediatric COVID-19 vaccine uptake using an mHealth tool: a randomized, controlled trial	
Study Description:	Site-level block-randomized trial	
Objectives:	Primary Objective:	Determine the effect of a parent-facing, vaccination decision-making mobile health (mHealth) tool on children's COVID-19 vaccine series completion
	Secondary Objective 1:	Determine the effect of a parent-facing, vaccination decision-making mHealth tool on children's COVID-19 vaccine series initiation
	Secondary Objective 2:	Determine the effect of a parent-facing, vaccination decision-making mHealth tool on parental attitude toward pediatric COVID-19 vaccination
Endpoints:	Primary Endpoint:	Proportion of children who complete COVID-19 vaccination, as verified in state, clinic, or participant-held records

**Secondary Endpoint 1:** Proportion of children who receive ≥1 dose of the COVID-19 vaccination series, as verified in state, clinic, or participant-held records

**Secondary Endpoint 2:** Change in enrolled parent/caregiver domain scores from baseline to immediately post-intervention on the modified WHO SAGE Vaccine Hesitancy Scale adapted for the COVID-19 Vaccine

**Study Population:** Custodial parents/caregivers with  $\geq 1$  child eligible for COVID-19 vaccination who has not yet received the vaccine at the time of study enrollment.

**Phase:** N/A

**Description of Sites/Facilities Enrolling Participants:** Enrolling sites will recruit participants. These sites will collaborate with outpatient practices within ECHO ISPCTN states that provide primary care services to children (<18 years old). Sites will serve a population base of at least 40% Medicaid/uninsured children, <60% non-Hispanic White children, or >40% of families residing in rural communities. Sites are encouraged, but not required, to have a high Spanish-speaking population.

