#### **WEEK 24 ASSESSMENT**

At week 24, participants will be sent a link to an assessment that asks for the vaccine status of eligible children.

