#### **11.4.3 ANALYSIS OF THE SECONDARY ENDPOINT(S)**

**Vaccine Series Initiation.** For each vaccine-eligible child, this secondary endpoint will be defined as whether or not the child initiates the COVID-19 vaccine series during the 16 weeks of study participation. Vaccine series initiation will be receipt of at least 1 valid dose of any COVID-19 vaccine product. Vaccine doses for series initiation will only be valid for study purposes if given within the 16 weeks of study participation. The statistical team will use a mixed model with the binomial distribution and the logit link to compare the two intervention groups with respect to the proportions of children who initiate COVID-19 vaccination, using site as a random effect and controlling for clustering by caregiver.

**Parental attitude toward pediatric COVID-19 vaccination.** The study team will evaluate parental attitude toward pediatric COVID-19 vaccination by using the vaccine hesitancy questionnaire that includes ten statements with ordinal responses using a 5-point Likert scale. At baseline and week 16, the study statisticians will generate summary statistics for each of the 10 questions for the two intervention groups. Similarly, the change in responses from baseline to end of study will be determined for each intervention group. The study statisticians will use the general linear mixed model to evaluate the intervention effect on responses to each measure at baseline and end of study, and they will use this model to evaluate the change in each measure by using site as a random effect. Within each intervention arm and for each statement, the study statisticians will use the Wilcoxon signed rank test to determine if the change in response from baseline to end of study is significantly different from zero.

---

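### Secondary endpoint 2 is named as domain scores that neither document defines, and nothing designates one deciding measure among the composite and ten items analysed instead

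*SAP*

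**What the plan says.** **Endpoint.** SAP 4.1 (Secondary Endpoints) names it as "Change in enrolled parent/caregiver domain scores from baseline to week 16" on the modified SAGE scale. Protocol 1.1, 4 and 10.1 also speak of domain scores.

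**Definition.** Beneath the endpoint, SAP 4.1 says "A composite vaccine hesitancy score will be the sum of the 10 items/statements after reverse coding items 1, 2, 3, 4, 6, 7, and 8", giving a range of 10 to 50 with higher values meaning more hesitancy. It then adds that "each statement/item will be treated as an individual outcome measure of hesitancy", each scored 1 to 5.

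**Analysis in the SAP.** Section 6.3.2 plans, for each item, a mean score chi-square test between arms and an adjusted linear mixed model. For the composite it plans a linear mixed model reporting the mean difference with a 95% CI. All are run in the ITT, mITT and PP populations; section 5.3 makes ITT primary. Section 5.2 sets a two-sided 0.05 level for every analysis unless stated otherwise.

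**Analysis in the protocol.** Section 11.4.3 covers only the ten statements. It plans mixed models for them, says that "the change in responses from baseline to end of study will be determined for each intervention group", and adds a Wilcoxon signed rank test for each statement within each arm.

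**Timing.** The synopsis (1.1) refers to "domain scores from baseline to immediately post-intervention". Protocol 4 and 10.1 and the SAP use week 16. Protocol Table 1 collects the hesitancy scale at baseline and week 16 only; the week 24 survey "asks for the vaccine status of eligible children".

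**The concern.** The term that names the endpoint has no counterpart in the analysis. No items are assigned to domains, and no domain scoring rule or domain-level model exists in either document. Outside this endpoint, the protocol uses the word for the components of the Health Belief Model.

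What the plan does analyse is eleven measures of one construct, and it does not say which of them answers secondary objective 2. A report could therefore follow the plan faithfully and rest a claim about parental attitude on one significant item. The last item in SAP Appendix A, for example, concerns diseases that have become uncommon. A difference on that item alone would be thin support for a statement about attitude to pediatric COVID-19 vaccination, yet nothing in the plan ranks it below the composite.

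**Working it through.** **Plan's own figures.** No sample size or power is stated for secondary endpoint 2. The stated 758 caregivers belong to the primary endpoint, and they reproduce. Per arm, (0.30×0.70 + 0.40×0.60) × (1.960 + 1.282)² / 0.10² × (1 + 0.60)/2 = 378.3, so 379 per arm and 758 in total; 758/0.85 gives 892. Nothing below alters these.

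**Counting the measures (SAP 6.3.2).**
- Between-arm measures: 10 items + 1 composite = 11.
- Planned analyses per population: 10 chi-square + 10 item models + 1 composite model = 21.
- Over three populations: 21 × 3 = 63.
- Protocol 11.4.3 adds 10 statements × 2 arms = 20 within-arm Wilcoxon tests, which do not compare the randomised arms.

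The 63 analyses are strongly dependent, because they use the same data, two methods per item and overlapping populations. An independence formula does not apply to them. The fair count for false positives is the 11 measures, once each, in the ITT population.

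**False-positive chance under no effect, each measure at two-sided 0.05.**
- Ten independent items: 1 − 0.95¹⁰ = 0.401.
- Eleven measures treated as independent: 1 − 0.95¹¹ = 0.431. This is too high, because the composite is the sum of the items.

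To respect that link, ten equally correlated standard normal item statistics were simulated 400,000 times as X_i = √r·C + √(1−r)·E_i. The composite statistic was ΣX_i / √(10 + 90r). The correlation r is an assumption, since the documents give none; the items are taken after reverse coding.

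| Assumed item correlation r | Any of 10 items | Any of 11 measures |
|---|---|---|
| 0 | 0.402 | 0.416 |
| 0.3 | 0.353 | 0.355 |
| 0.5 | 0.287 | 0.287 |
| 0.7 | 0.214 | 0.214 |
| 0.9 | 0.128 | 0.128 |

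The first row agrees with the exact 0.401 for ten independent items. Almost all of the inflation comes from the items; the composite adds little. One designated test has a rate of 0.05.

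**Time points side by side.**
- Protocol 4, protocol 10.1, SAP 4.1 and SAP 6.3.2: week 16.
- Protocol 1.1: just after the intervention, which the same synopsis describes as a 24-week exposure.
- Protocol 11.4.3: end of study, which section 5.3 places at 29 weeks. The same paragraph of 11.4.3 also refers to baseline and week 16.
- Data available after baseline (Table 1): week 16 only.

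Read literally, the phrases in 1.1 and 11.4.3 describe changes for which no data are collected.

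**The case against.** The best case for the plan is that SAP 4.1 already defines a score. The composite comes first in the definition, with its items, coding, range and direction, and the items follow as an addition. SAP 6.3.2 gives the composite its own model, mean difference and interval. The protocol leaves analytical detail to the SAP, so the composite is the natural operational endpoint and the word domain is a leftover label. The objection continues that multiplicity within one secondary questionnaire is largely a matter of convention in a trial that is not FDA-regulated, and that for the composite the SAP promises an estimate and interval and names no explicit test.

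Much of this stands. The composite is the most natural candidate, and its 0.05 test follows only from the general default in SAP 5.2. But the same definition makes every item an outcome measure in its own right, the items do receive explicit tests, and protocol 11.4.3 omits the composite altogether. Natural order in a paragraph is not a designation.

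On timing the objection largely succeeds. Scheduled notifications end at about week 16 (8 weeks plus 2 months), which gives the synopsis phrase a possible reading. The protocol's change log records the former post assessment becoming the week 16 assessment, so the stray phrases look like residue. Since the scale is collected at only one later time, an analyst has no choice of time point to exploit. The mismatch is editorial.

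**Conclusion.** The point holds as a gap in designation. Secondary endpoint 2 is named by a score that does not exist in the plan, and no rule says which of eleven between-arm measures decides secondary objective 2. The size is about a 13% to 42% chance of at least one nominally significant result under no effect, against 5% for one test. That range rests wholly on the assumed item correlation (0.9 to 0) and on equal correlation among items. The upper end requires independent items, which is implausible for statements summed into one score.

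Some stronger readings are tempting and are not supported:
- That success could be claimed in any of three populations. SAP 5.3 makes ITT primary and the other two additional, so the percentages do not multiply.
- That the plan expressly allows any single item to suffice. It states no success rule for this objective; the weakness is that silence.
- That the time-point wording opens a choice of analysis. It does not, because week 16 is the only post-baseline collection.
- That the main result is at risk. The primary endpoint, its 0.05 level and the 758/892 sample size are untouched.

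This should be settled before data lock.

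**What to change.** 1. In protocol 1.1, 4 and 10.1 and SAP 4.1, replace the reference to domain scores with the composite score (10–50).
2. State in SAP 6.3.2 and protocol 11.4.3 that the single test for secondary objective 2 is the between-arm difference in the week 16 composite, adjusted for the baseline composite in the linear mixed model already planned, in the ITT population. SAP 6.3.2 does not now say whether the models use the change or the week 16 value; this wording settles that.
3. Label as descriptive, with no significance claim, the item-level chi-square and mixed-model results (SAP 6.3.2, protocol 11.4.3) and the within-arm Wilcoxon results (protocol 11.4.3). Estimates with intervals can still be shown.
4. As an editorial alignment, change the time-point phrases in protocol 1.1 and 11.4.3 to week 16.

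If the sponsor wants item-level claims, all 11 measures would need adjustment. Bonferroni gives 0.05/11 = 0.0045 per test, with simulated family-wise error of 0.048 at zero correlation and 0.015 at 0.9. That controls the error but is conservative for correlated items, and it would also hold the composite to the stricter level.

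Cost: a small amendment to both documents, with IRB review of the protocol change, and the loss of item-level significance claims. No new data or new model are needed.

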5. STATISTICAL PRINCIPALS

5.1 GENERAL APPROACH

The statistical team will conduct all statistical analyses following the statistical principles for clinical trials as specified in ICH Statistical Principles for Clinical Trials (ICH Topic E9). The study team will describe and justify any deviations from the planned analyses in the final integrated clinical study report. The study team will present all study data and summary tables for the overall study and by study sites.

The statistical team will summarize descriptive statistics for continuous data by using mean and standard deviation or median and interquartile range, as appropriate. The team will also summarize categorical data by using frequency and percent.

The statistical software package SAS Version 9.4 or higher (SAS Institute, Cary, NC, USA) or STATA version 14 or higher (Stata Statistical Software, College Station, TX: StatCorp LLC) will be used to perform all analyses and to summarize data.

5.2 STATISTICAL SIGNIFICANCE AND CONFIDENCE INTERVALS

Unless otherwise specified, statistical tests will be 2-sided for all analyses and the null hypothesis will be rejected at the significance level of $\alpha = 0.05$. P-values will be rounded to four decimal places before assessing statistical significance. All confidence intervals presented will be 95% and two-sided.

5.3 POPULATIONS FOR ANALYSES

This study will have three analysis populations:

1. ITT population – This population will include all participants randomized into the study.
2. Modified ITT (mITT) population – This population will include all participants who are randomized into the study, were eligible for the study, and completed at least one session in the app involving the use of at least one pathway.
3. Per-protocol (PP) population - This population will include all participants in the mITT population who were maintained in the study for the full 27 weeks.

The primary population for analysis will be the ITT population. Study statisticians will perform additional analyses on the PP and mITT populations.

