**Description of Study Intervention:**

- **Vaccine Uptake App:** 24-week (8 weeks with weekly push notifications; 2 monthly push notifications for 2 months [1 notification per month]; 8 weeks without) exposure to a mobile phone application (app) designed to improve parental knowledge, attitudes, and self-efficacy regarding pediatric COVID-19 vaccination. The app will address logistical and motivational barriers to pediatric COVID-19 vaccination. Participants will also receive eight weekly nudges (cues to action) regarding vaccinating their child that will be sent to participants via push notifications to their mobile devices. Through branching logic, users will access content tailored to their COVID-19 vaccine knowledge and confidence gaps, locality, degree of rurality-urbanicity, primary language (English/Spanish), race/ethnicity, and child's age.
- **General Health App:** 24-week (8 weeks with weekly push notifications; 2 monthly push notifications for 2 months [1 notification per month]; 8 weeks without) exposure to a mobile phone app designed to provide information on general pediatric health and infection prevention and mitigation strategies based on recommendations from the American Academy of Pediatrics (AAP) and the Centers for Disease Control and Prevention (CDC). Nudges regarding these topics will be sent to participants via push notifications to their mobile devices.

[figure not shown]
**Study Duration:** 24 months (6 months study start-up; up to 8 months rolling enrollment; 7 months final participants' completion; 3 months analysis)

**Title:** Improving pediatric COVID-19 vaccine uptake using an mHealth tool: a randomized, controlled trial

**PI:** [name]

**Participant** 28 weeks (8 weeks with weekly push notifications; 2 monthly push notifications for 2 months  
**Duration:** [1 notification per month]; 8 weeks without notifications; 4 weeks participant vaccine status follow-up)

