### 5.3 END OF STUDY DEFINITION

The study will end for the participant after they have reached 29 weeks of enrollment and either completed their 24-week assessment or failed to complete it by week 29.

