#### **PARTICIPANT VACCINE STATUS FOLLOW-UP**

Study staff will assess COVID-19 vaccination status as noted above. For any child who is not card-verified at the 8-, 16-, or 24-week assessment, site coordinators/study team members will review the child's vaccination records in their clinic's electronic medical record system and/or the state immunization registry beginning at Week 25 to determine COVID-19 vaccine status.

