## 10. STUDY ASSESSMENTS AND PROCEDURES

### 10.1 EFFICACY ASSESSMENTS

The primary endpoint is child initiation and completion of COVID-19 vaccination by the end of week 24 post caregiver randomization. Verification of vaccine receipt will occur by any of the following methods:

1. Photograph of the child's vaccine card, furnished by the caregiver
2. Medical records documentation of child vaccine receipt
3. Recorded vaccine receipt in the appropriate state vaccine registry

**Title:** Improving pediatric COVID-19 vaccine uptake using an mHealth tool: a randomized, controlled trial

**PI:** [name]

**Secondary endpoint #1** is child receipt of  $\geq 1$  dose of the COVID-19 vaccination series by the end of week 24 post caregiver randomization. Verification of vaccine receipt will be the same as for the primary endpoint.

**Secondary endpoint #2** is enrolled caregiver domain scores on the modified SAGE Vaccine Hesitancy Scale adapted for the COVID-19 Vaccine from baseline and the end of week 16 post caregiver randomization. Caregiver participants will complete this survey electronically.

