### 11.4.2 ANALYSIS OF THE PRIMARY EFFICACY ENDPOINT(S)

**COVID-19 Vaccine Series Completion.** For each vaccine-eligible child, the primary endpoint will be whether or not the child initiates and completes the COVID-19 vaccine series during the 24 weeks of the intervention period. The study team will define vaccine series completion as per the current ACIP guidance for the vaccine product. For children who receive a product that requires more than 2 doses for the primary series, receipt of up to 3 doses will be considered complete. Vaccine doses will only be valid for study purposes if given within the 24 weeks of study participation. Additional doses, when required for primary series completion, will only be valid if they are in accordance with ACIP-recommended interval minus a 4-day grace period, in accordance with recommendations of the ACIP. Also, per ACIP, there will be no maximum interval between valid doses. Incorrect second vaccine product (i.e., mixed series) will be invalid for study purposes. The statistical team will use a mixed model with the binomial distribution and the logit link to compare the two intervention groups with respect to the proportions of children who complete COVID-19 vaccination, using a site random effect and controlling for clustering by caregiver.

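### The per-protocol set requires 27 weeks in the study, which agrees with neither the 24-week endpoint window nor the 28- and 29-week participant durations stated elsewhere

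*SAP*

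**What the plan says.** SAP 5.3 and protocol 11.3 give the same PP definition: members of the modified-ITT (mITT) set who were "maintained in the study for the full 27 weeks". Neither document defines what it means to be maintained in the study. ITT is the primary population and PP is additional, but SAP 6.2, 6.3.1 and 6.3.2 run the completion, initiation and hesitancy analyses on all three sets.

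The other time points in the documents are these:

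- **Endpoint window, 24 weeks.** Protocol 11.4.2 (repeated in SAP 6.2) states: "Vaccine doses will only be valid for study purposes if given within the 24 weeks of study participation". Protocol 10.1 sets the primary endpoint "by the end of week 24 post caregiver randomization". The app exposure also lasts 24 weeks and the last survey is at week 24.
- **Participant duration, 28 weeks.** The synopsis in protocol 1.1 gives "28 weeks (8 weeks with weekly push notifications" and further components, the last being "4 weeks participant vaccine status follow-up".
- **End of study, 29 weeks.** Under protocol 5.3 a participant's study ends "after they have reached 29 weeks of enrollment and either completed their 24-week assessment or failed to complete it by week 29".
- **Verification.** For children not verified by card at the week 8, 16 or 24 assessment, protocol 7.5.3 has staff review the clinic record or state registry "beginning at Week 25 to determine COVID-19 vaccine status".

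SAP section 1 says that the SAP applies to protocol Version 09. The current protocol is Version 10, whose change summary records an extension of vaccine status follow-up to week 29.

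**The concern.** A per-protocol rule should reflect adherence, or whether the endpoint could be determined. A retention threshold three weeks after the dose window has closed does neither directly. Take a caregiver whose children's completed series was card-verified at week 16 and who withdraws in week 26. The 24-week outcome is known and cannot change, yet the literal rule removes that family from every PP analysis.

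The clause is also hard to program. The analyst must decide whether 27 weeks stands as written or was meant to be one of the stated lengths, and whether being maintained means not withdrawing (protocol 9.1), not being lost to follow-up (protocol 9.2), or both. The trial is unmasked (SAP 3.2.2), so these decisions are better fixed in writing before data lock than made with the data in view.

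**Working it through.** **1. The plan's own figures.** The synopsis itemises the participant's time as 8 weeks of weekly notifications, 2 months of monthly notifications, 8 weeks without notifications and 4 weeks of vaccine status follow-up. Its 24-week exposure has the first three parts, so the 2 months count as 8 weeks:

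- exposure: 8 + 8 + 8 = 24 weeks
- participation: 24 + 4 = 28 weeks, as the synopsis states

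The number randomized also reproduces: 758 / (1 − 0.15) = 891.8, rounded up to 892.

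**2. The 27 weeks against each stated time point.**

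| Time point | Source | Weeks | 27 minus this |
|---|---|---|---|
| Dose window, primary endpoint, last survey | Protocol 7.5.3, 10.1, 11.4.2; SAP 6.2 | 24 | +3 |
| Participant duration | Protocol 1.1 | 28 | −1 |
| End of study | Protocol 5.3 | 29 | −2 |

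Week 27 lies inside the verification period that opens at week 25, but it is not the end of that period under either stated length.

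**3. Who is removed under a literal reading.** Consider a caregiver in the mITT set who withdraws or is removed after week 24 and before week 27.

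- *Status already verified by card:* the 24-week endpoint is known, and the caregiver is dropped.
- *Status not verified by card:* the endpoint depends on record review from week 25. It may or may not have been determined by the time of withdrawal. The documents do not say whether review continues after consent is withdrawn.

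Only the first group, and those in the second whose review was already complete, lose a known endpoint.

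**4. Size.** The documents give no withdrawal rate over time. *Assumptions:* constant withdrawal hazard; cumulative withdrawal d of 5%, 10% or 15% by week 29; 892 caregivers randomized.

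- hazard h = −ln(1 − d) / 29 per week
- fraction withdrawing between week 24 and week T = exp(−24h) − exp(−Th)

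For d = 0.10: h = 0.10536 / 29 = 0.003633; exp(−24h) = 0.9165; exp(−27h) = 0.9066; difference 0.0099; times 892 = 8.9 caregivers.

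| Withdrawn by week 29 | Weeks 24–27 | Weeks 24–28 | Weeks 24–29 |
|---|---|---|---|
| 5% | 4.5 (0.5%) | 6.0 | 7.5 |
| 10% | 8.9 (1.0%) | 11.8 | 14.7 |
| 15% | 13.0 (1.5%) | 17.3 | 21.5 |

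Under these assumptions the weeks 24–27 column is an upper bound on wrongly removed caregivers, since they must also belong to the mITT set and have determined status. If withdrawals clustered just after the week 24 survey, the count could be higher. The last two columns show that moving the threshold to 28 or 29 weeks would remove more families, not fewer.

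**5. What does not change.** The primary analysis uses ITT. The sample-size calculation (379 caregivers per arm, 758 in total, 892 randomized) contains no 27-week retention term, so it and the power are unaffected.

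**The case against.** The strongest reply is that this is a consistency slip in a supporting analysis. PP membership already requires eligibility and at least one app session using a pathway, which matches the compliance definition in protocol 8.4; the 27-week clause only adds retention. Few caregivers are likely to be affected. The figure may also be left over from before Version 10 lengthened follow-up, although the documents do not show this. The point about size stands and limits the weight of the concern. The possible origin does not remove the mismatch, because protocol 11.3 in Version 10 still says 27.

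A reader might infer three stronger things, none of which the documents support:

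- *That week 27 corresponds to nothing in the trial, or that no event occurs then.* It falls within vaccine status follow-up. The cell marks of the participant schedule (protocol 1.3.2) and the schema are not legible in the text available, so absence of an event cannot be claimed.
- *That everyone who withdraws in weeks 25 or 26 has an observed endpoint.* The dose window closes at week 24, but ascertainment does not. The plan expects only 30% to 40% of children to complete the series, so many are likely to depend on record review, and retention past week 24 has a purpose for them.
- *That keeping a caregiver who answers no survey is a defect.* The vaccination endpoints can be verified from the medical record or registry without a survey, and protocol 9.2 defines loss to follow-up by unconfirmed vaccination status.

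It can also be said that requiring determined status conditions PP on outcome availability, and that one reconciled follow-up length would be an alternative. That is a fair choice to raise. However, a longer threshold removes more families with known outcomes, and counting a completed review that finds no dose as determined keeps the set from being selected towards vaccinated children.

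**Conclusion.** The concern holds in a limited form. The 27-week clause, present in both documents, agrees with none of the 24-, 28- and 29-week time points, and read literally it excludes some caregivers whose children's 24-week status is already verified. The number is probably small: at most about 4.5 to 13 of 892 (0.5% to 1.5%), resting entirely on the assumed 5% to 15% withdrawal by week 29 and a constant hazard. The consequence is confined to the additional PP analyses. The clause should be corrected because it decides membership for all of them and cannot be applied without interpretation, not because it threatens the main conclusion of the trial.

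**What to change.** In SAP 5.3 and protocol 11.3, replace the 27-week clause with a definition along these lines: caregivers in the mITT set who neither withdrew nor were removed before the end of week 24, and whose children's vaccination status for the 24-week window was determined from a card, the medical record or the registry. State that a completed record review finding no dose counts as determined.

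In the same revision, reconcile the 28-week participant duration in protocol 1.1 with the 29 weeks in protocol 5.3, and bring the SAP's reference and time points into line with protocol Version 10.

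The cost is a short text edit in each document before data lock. It needs no new data collection and no change to the sample size or the primary analysis.
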